#### *F.6.6 Clinical Event Committee*

A clinical event committee (CEC) will be established. The CEC is an independent committee made up of clinicians (interventional) with pertinent expertise who are not participants in the study and who do not have any other real or potential conflicts of interest. The CEC will meet periodically to review and adjudicate all MDEs, deaths and all DTAA ruptures that occur throughout the conduct of the clinical trial. A charter will be developed that will detail the criteria for selected complications and clinical events that need to be adjudicated as well as the CEC composition, duties, procedures and adjudication rules and meeting frequency.

#### *F.6.7 Data Monitoring Committee*

A Data Monitoring Committee (DMC) will be established. The DMC is composed of several members with pertinent expertise who are not participants or directly involved in the conduct of the trial.

The responsibility of the DMC is to evaluate safety data during the course of the trial and to advise Medtronic about the continuing safety of the trial to ensure the wellbeing of the current participants and those yet to be enrolled as well as the continuing validity and scientific merit of the trial.

Based on the safety data, the DMC may recommend that Medtronic modifies or stops the trial. DMC composition, duties, procedures, deliberation rules are detailed and documented in the DMC Charter.

In addition to DMC members an Independent Medical Monitor will be appointed. Medtronic will provide listings of all Adverse Events and Device Deficiencies to this Independent Medical Monitor on a monthly basis to evaluate safety of the study device. All events, including any device related events will be reviewed on a case by case base by the Independent Medical Monitor. In case of a safety concern the Independent Medical Monitor can trigger a DMC meeting.

Trial data will be reviewed on a periodic basis as defined in the DMC Charter.

#### *F.6.8 Emergency contact details in case of serious AEs*

In case of an immediately reportable Adverse Event the investigators can contact Medtronic. Contact details of Medtronic Study Management are given in the Investigational Site File. In case the investigator requires information in a medical emergency situation the investigator can contact the Medical Expert. Contact details of Medical Expert are given in the Investigational Site File.

## **F.7 Subject accountability**

Every subject should be encouraged to remain in the study until they have completed the required follow up per the study protocol.

If a subject is withdrawn from the clinical study, the reason for withdrawal shall be recorded on the appropriate eCRF and in the subject's hospital record. If discontinuation is because of safety or lack of effectiveness, the subject shall be asked to be followed for collecting safety

data outside the clinical study. Subjects will not be replaced in case of premature study discontinuation.

#### *F.7.1 Criteria and procedures for exit from study*

The Study Exit Form should be completed at the time a subject is exited from the study. A subject will be considered to have exited from the study for any of the following reasons:

- Subject completes follow-ups required by the investigational plan
- Subject dies
- Subject requests to be withdrawn
- Investigator requests that subject be withdrawn to protect the welfare of the subject
- Subject is lost to follow-up
- Other (specify)

#### *F.7.2 Study Withdrawal*

Subjects may withdraw from the study at any time and for any reason. If a subject decides to withdraw from the study, the investigator will document the reason for withdrawal and indicate any relationship of the withdrawal to the study or products being investigated in the subject's hospital record in the subjects file. If discontinuation is because of safety or lack of effectiveness, the subject shall be asked to be followed for collecting safety data outside the clinical study. In addition, subject withdrawal will be documented on Study Exit eCRF.

If the subject is unable to be followed, the investigator has to notify the sponsor in a timely manner.

#### *F.7.3 Missed follow-up*

A missed follow-up visit should be documented by the investigator and reported in the eCRF, including the reason. If the date the subject is last known to be alive is obtained, this should be recorded on the Follow-up visit eCRF and the method of obtaining this date should be documented in the medical record.

#### *F.7.4 Lost-to-follow-up*

A subject may be considered lost to follow-up once there are 3 documented attempts by the investigator and/or research staff to contact the subject. The third attempt should be made by mail to the subject and phone call or mail to the subject's emergency contact.

#### *F.7.5 Medical care after study exit*

After study exit the subjects will be followed as per routine standard of care by the investigational site or a treating physician which might be in line with the guidelines described in the ESC (European Society of Cardiology) Guidelines on the diagnosis and treatment of aortic diseases.

Relevant medical records may be made available by the investigational sites for the treating physician per local laws and regulations if needed for further subject treatment. As per local law and regulation the trial investigator may be contacted by the treating physician in case of questions related to the study device and treatment.

## **F.8 Study deviations and CIP changes**

A study deviation is an event where the investigator or investigation site personnel did not conduct the clinical study according to the Clinical Investigation Plan or Clinical Investigation Agreement. The investigator is not allowed to deviate from the above mentioned documents except with prior approval and under emergency circumstances. All deviations shall be documented and explained, regardless the reason for the deviation.

Deviations will be recorded at the site and reported to Medtronic on the Study Deviation eCRF.

Medtronic shall review reports of deviations upon receipt and determine appropriate action, including any associated Ethics Committee (EC), and/or regulatory reporting requirements. The clinical study team shall follow up with the center on the implementation and closure of any preventive or corrective actions. Deviations will be entered into a database to allow a comprehensive review on a quarterly basis for identifying trends that warrant additional preventive or corrective actions to mitigate further occurrence. This review shall be conducted by clinical study management.

Specific examples of deviations include but are not limited to:

- Failure to obtain informed consent prior to participation
- Incorrect version of the informed consent form used
- No EC approval before the start of the study
- Enrolled subject did not meet inclusion/exclusion criteria
- CIP required testing and/or measurements not done or incorrectly done
- Subject did not attend follow up visit or follow up visit outside window
- Unauthorized use of investigational devices
- Adverse event not reported by investigators in the required time frame as specified in the CIP
- Control of study devices not maintained
- Source data lost or unavailable
- Enrollment of subjects during elapse of EC approval
- Exceeding inclusion limits specified by Medtronic
- Subject not implanted according to the Instructions for Use.

Medtronic will assess the significance of all deviations and evaluate the need to amend the Clinical Investigation Plan or to early terminate the investigation, in accordance with Medtronic SOPs.

In case a deviation may occur multiple times over the course of the clinical study in the same subject because of a permanent change (e.g. CT scan/MRI with contrast not performed at Follow Up visits due to renal insufficiency developed post-operatively) deviation should be reported only once per subject at the time of first occurrence.

#### *F.8.1 Request for approval of study deviations*

The investigator shall obtain documented approval from Medtronic, before implementation, for any change in- or deviation from the Clinical Investigation Plan. In case of study deviations that can affect the subject's rights, safety and well-being or the scientific integrity of the clinical study, approval from the EC and Regulatory Authority must also be obtained before implementation. The investigator shall timely contact the Clinical Study Manager for review of the proposed change/deviation.

Prior approval is not always realistic in situations where unforeseen circumstances are beyond the investigator's control. However, also in these cases, the event is considered a deviation, and shall be reported.

In any emergency situation the investigator shall exercise his/her judgment to safeguard the subject's interest. Such deviations from the Clinical Investigation Plan do not require the prior approval of Medtronic. The investigator shall report the deviation as soon as possible to Medtronic and the reviewing EC, if applicable. Medtronic will inform the Regulatory Authorities, if required.

#### *F.8.2 Reporting requirements for study deviations*

The investigator shall adhere to EC requirements and procedures for reporting study deviations.

Medtronic is responsible for analyzing deviations, assessing their significance, and identifying any additional corrective and/or preventive actions (e.g. amend the CIP, additional training, terminate the study, etc.). Repetitive or serious investigator compliance issues may result in the need to initiate a corrective action plan, and in some cases freeze enrolment or ultimately terminate the investigator's participation in the clinical study:

- Non-compliance to obtain patient informed consent
- Non-compliance to the inclusion/exclusion criteria
- Failure to follow subjects per scheduled follow-ups
- Failure to submit data in a timely manner
- Failure to follow-up with findings on monitoring reports
- EC approval expiration
- EC suspension of the center

If a center is terminated or suspended, no additional enrollments will be allowed at the center. Unused investigational product allocated to the center will be returned to Medtronic.

Medtronic will provide investigation site-specific reports to the investigators on a periodic basis summarizing information on deviations that occurred at the investigation site.

### *F.8.3 Amendments to the Clinical Investigation Plan*

The investigator may propose any appropriate modification(s) of the Clinical Investigation Plan or investigational device/product or investigational device/product use. Medtronic will review this proposal and decide whether the modification(s) will be implemented. Medtronic will submit any significant amendment to the Clinical Investigation Plan, including a justification for this amendment, to the appropriate Regulatory Authorities and to the investigators to obtain approval from their EC and Regulatory Authorities, if required. The investigator will only implement the amendment after approval of the EC, Regulatory Authority (if required) and sponsor. Administrative amendments to the Clinical Investigation Plan will be submitted to the EC and Regulatory Authority (if required) for notification. Furthermore investigators shall sign any approved amendment for agreement.

## **G QUALITY CONTROL PROCEDURES**

### **G.1 Procedures for database management**

#### *G.1.1 Data collection*

The investigator must ensure accuracy, completeness and timeliness of the data reported in the CRFs and in all other required reports. Data reported on the CRFs which are derived from source documents must be consistent with the source documents and discrepancies need to be justified in a documented rationale, signed and dated by the (principal) investigator, and filed in the subject medical file.

Only authorized persons can complete CRFs. CRFs shall be signed by investigators (physicians only) as specified on the Delegated Tasks List included in the Investigator Site File.

The Electronic Data Capture (EDC) system maintains an audit trail on entries, changes or corrections in CRFs. If a person is only authorized to complete CRFs or to make changes to an already signed CRF, the investigator shall re-sign this CRF.

Any source documentation as well as any imaging (e.g., procedure reports, imaging material, lab reports, death certificates, autopsy reports) that is sent to the sponsor should have all subject identifiers removed and replaced with the subject's study ID.

A paper copy of the eCRFs as well as access to the EDC system will be provided to the investigation site prior to subject enrollment.

### *G.1.2 Source data to be directly recorded on the Case Report Forms*

All data reported on the eCRFs shall be derived from source documents and be consistent with these source, and any discrepancies shall be explained in writing. There are no data that will be recorded directly on the eCRF without corroborating source documentation.

### *G.1.3 Time windows for completion and submission of Case Report Forms*

All data entry should be completed as soon as possible after the visit takes place. Adverse event and device deficiencies should be reported as described in the section F.6.

### *G.1.4 Data review and processing*

Data management will be done according to Medtronic SOPs and the Data Management Plan for this clinical study. These documents will be made available on request.

All collected data will be reviewed for completeness, correctness and consistency. In case of issues, queries will be sent to the investigator to complete, correct or comment the data.

## **G.2 Monitoring procedures**

A site qualification visit may be conducted by Medtronic personnel (or designees) to review the clinical investigational plan and regulatory and study requirements with the investigator and study personnel. A site initiation visit will be performed after it has been verified that the site is prepared for the study and that the site requirements for study participation are met.

Monitoring visits will be conducted at the start, during and at the closure of the clinical study in accordance with Medtronic SOPs and the Monitoring Plan. Frequency and timing of monitoring visits shall be determined by the Sponsor for each site based on enrollment rate and volume, study compliance and findings from previous visits.

It will be verified whether signed and dated Informed Consent Forms have been obtained from each subject before any clinical study related procedures are undertaken. Medtronic or designee will conduct site monitoring visits to monitor compliance with the protocol and adherence to the data collection procedures, to assess the accuracy and completeness of submitted clinical data, and to verify that records and documents are being properly maintained for the duration of the study.

### *G.2.1 Accessibility of investigation site staff and study materials*

The principal investigator(s), his/her delegate(s) and the study coordinator(s) shall be accessible to Medtronic field personnel and the Clinical Study Manager. This accessibility is of particular importance for reviewing data in the Case Report Form (CRF). Direct access to subject medical files for source data verification will need to be granted and prepared prior to any monitoring visits. If direct access cannot be provided per local laws and regulations, certified copies need to be made available or monitor needs to obtain access by reviewing alongside with study staff.

### *G.2.2 Audits and investigation site inspections*

In addition to regular monitoring visits, Medtronic may conduct audits at participating investigation sites. The purpose of an audit is to verify the adequate performance of the clinical study related activities. Independent of the employees involved in the clinical study. Regulatory bodies may also perform inspections at participating investigation sites. Any Regulatory Authority inspection announcements shall be forwarded immediately to the Clinical Study Manager.

The investigator and/or institution shall permit Medtronic and regulatory bodies direct access to source data and documents, taking into account any restrictions due to local law, to perform clinical study-related monitoring, audits, EC review, and regulatory inspections.

### G.3 Study suspension or early termination

#### G.3.1 Early study suspension or termination

Medtronic or Regulatory Authority may decide to suspend or prematurely terminate the clinical study (e.g. if information becomes available that the risk to study subject is higher than initially indicated, if interim analysis indicates that the results significantly differ from the clinical study objectives or statistical endpoints). If the clinical study is terminated prematurely or suspended, Medtronic shall promptly inform the investigators of the termination or suspension and the reason(s) for this. The investigator shall then promptly inform the reviewing EC and the study subjects. Medtronic will inform the Regulatory Authority(ies) where required by applicable regulatory requirements.

#### G.3.2 Early investigation site suspension or termination

Medtronic, EC or Regulatory Authority may decide to suspend or prematurely terminate an investigation site (e.g. in case of expiring approval of the reviewing EC, non-compliance to the Clinical Investigation Plan or lack of enrollment). If an investigation site is suspended or prematurely terminated, Medtronic shall promptly inform the investigator(s) of the termination or suspension and the reason(s) for this. The investigator shall then promptly inform the reviewing EC and the study subjects or their legal representative.

If an investigation site is suspended or prematurely terminated:

- Medtronic shall promptly inform the clinical investigator(s) of the termination or suspension and the reason(s) for this
- The investigator shall then promptly inform the reviewing EC
- The investigator shall then promptly inform study subjects
- The investigator agreement will be terminated
- The investigator will inform the institution (where required by applicable regulatory requirements)
- Medtronic will inform the Regulatory Authority(ies) (where required by applicable regulatory requirements)

When the risks are found to outweigh the potential benefits or when there is conclusive proof of definite outcomes, investigators must assess whether to continue, modify or immediately stop the clinical study in the respective investigation site and immediately inform the sponsor and EC, if applicable.

#### G.3.3 Subject follow-up in case of termination

If the study is terminated early, subjects will be followed as per routine standard of care by the investigational site or a treating physician which might be in line with the guidelines described in the ESC (European Society of Cardiology) Guidelines on the diagnosis and treatment of aortic diseases.

After study termination relevant medical records may be made available by the investigational sites for the treating physician per local laws and regulations if needed for further subject treatment. As per local law and regulation the trial investigator may be contacted by the treating physician in case of questions related to the study device and treatment.

### G.4 Study close out

Prior to completion of study close out, all data must be entered and monitored in the EDC system.

Medtronic and/or its designees will notify the site of the intention to close the study. Study close out visits may be performed. During these visits, the monitors will ensure that the investigator's regulatory files are up to date and complete and that any outstanding issues from previous visits have been resolved. Medtronic will notify and inform the site(s) that all requirements have been met with a study closure letter.

If required, EC and/or Regulatory Authority will be informed by Medtronic about the study close out.

## H DATA ANALYSIS AND REPORTING

Any deviations from this section and/or the Statistical Analysis Plan will be described and justified in the Final Clinical Study Report, as appropriate.

### H.1 Analysis of clinical data

The Valiant Evo International Trial is not hypothesis driven. All endpoints will be analyzed descriptively. The limitation of the design for this study is that there are no pass/fail criteria from a statistical hypothesis testing.

All endpoints will be analyzed descriptively. Event rates corresponding to the primary endpoint of the study will be analyzed by calculating the distribution frequencies and the associated 1-sided 95% confidence limits using an exact method.

In general, qualitative parameters will be described by their distribution frequencies; quantitative parameters will be described by their mean, standard deviation, minimum, maximum, median, and number of subjects with assessable data.

The survival from all-cause mortality over one year time or longer will be described by the Kaplan-Meier survival curve and the associated Kaplan-Meier estimate will be calculated along with its standard error using the Greenwood method.

For events, such as AEs, deaths and secondary procedures, that can occur or are observed at any time during the study, no time window will be applied. For such events, an event that occurs “within 30 days” is an event that takes place between Days 0 to 30, inclusive. Similarly, an event that occurs “within 365 days” is an event occurring between Day 0 to Day 365, inclusive. Date of event onset will be used to determine when the event occurred. Day 0 is referring to the day of index procedure.

For image-based assessments, such as stent-graft endoleak, patency and device deficiencies, the following time windows will be applied for by-visit data summaries:

**Table H-1: Time Windows for Statistical Analyses**

Study Visit	Target Day	Time Window
Implant	0 days	Day 0
1 Month	30 days	1 – 90 days
12 Months	365	305 – 548 Days

If there are two or more assessments in the same time window, then the assessment closest to the target day will be used in the analysis of event rate at a given time point. In addition to endpoints, summaries of subject disposition, demographics, baseline characteristics, and subject accountability will be provided.

Subset analysis will be performed by-sex separately for the primary endpoint descriptively and reviewed for clinical significant difference.

All analysis will be performed on the modified intent-to-treat analysis set, which includes all included subjects. Subjects will be considered as included in the study as described in section F.1.

During statistical analysis, imputation of missing data will not be performed except for data related to the onset date of an adverse event or a death. In cases where the onset date of an event or a death is incomplete and unresolvable via data query, the 15th day of the known month or July 1st of the known year will be used.

Statistical analyses for this study will be performed using the Statistical Analysis System (SAS) for Windows (Version 9.1 or higher) or other widely-accepted statistical or graphical software.

Analysis for the Regulatory Submission:

For the primary endpoint, which is defined as the proportion of subjects experiencing an MDE within 30 days post-implantation, a 1-sided 95% confidence interval using the exact method (Clopper-Pearson) will be constructed in addition to event count frequency.

Additionally, a two-sided 95% confidence interval will also be provided. The SAS procedure PROC FREQ will be used for calculation of the confidence interval.

The analysis for the regulatory submission will take place when the first 47 subjects have been implanted with the study device for at least 30 days except that a subject expires early. Endpoints will be analyzed for these 47 included subjects as defined in Section C.2.

Interim Analysis:

No interim analysis is planned prior to the CE Mark Submission.

Annual Report:

An annual report will be provided for all enrolled subjects at the time of reporting according to requirements from notified bodies in the European Union and regulatory agencies in various countries.

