## A SYNOPSIS

Title	Valiant Evo International Clinical Trial
Investigational Device	Valiant™ Evo Thoracic Stent Graft System
Study Design	The Valiant Evo International Clinical Trial is a prospective, multi-center, pre-market, non-randomized, single-arm trial.
Purpose	
The purpose of the Valiant Evo International Clinical Trial is to demonstrate the safety and effectiveness of the Valiant Evo Thoracic Stent Graft System in subjects with a descending thoracic aortic aneurysm (DTAA) who are candidates for endovascular repair. The Valiant Evo International Clinical Trial is a first-in human experience with the objective to provide clinical data for supporting CE marking via case series and descriptive statistics.
 
Data collected during this trial may also be used in conjunction with data collected during a concurrently enrolling IDE trial to support commercial approval of the Valiant Evo Thoracic Stent Graft System in the United States.

Primary objective	The primary objective is to demonstrate the safety and effectiveness of the Valiant Evo Thoracic Stent Graft System in subjects with a DTAA who are candidates for endovascular repair.
Secondary objective	
Secondary objectives include descriptive analyses of secondary endpoints as well as acute procedural observations and clinical utility measures.
 
Safety and effectiveness data will be collected over a one year period following endograft implantation.

Primary Endpoint	
Composite safety and effectiveness endpoint that is based on the proportion of subjects who experienced:
 
 
(a) Access and/or deployment failures; and/or
 
(b) Major device effect (MDE) within 30 days post index procedure
 
 
MDEs include the occurrence of any of the following and are defined in Appendix L.2.1:
 
 
• Device-related secondary procedures
 
• Device-related mortality
 
• Conversion to open surgery
 
• Thoracic aortic aneurysm rupture
 
 
An independent Clinical Events Committee (CEC) will be established to adjudicate MDEs.

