## C.2 Clinical endpoints

### C.2.1 Primary endpoint

The primary objective will be assessed by the composite safety and effectiveness endpoint that is based on the proportion of subjects who experienced:

- (a) Access and/or deployment failures; and/or
- (b) MDE within 30 days post index procedure

MDEs include the occurrence of any of the following:

- Device-related secondary procedures
- Device-related mortality
- Conversion to open surgery
- Thoracic aortic aneurysm rupture

Detailed definitions of MDEs are defined in Appendix L. 2.1.

An independent CEC will be established to adjudicate MDEs.

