### C.7 Sample size

A sample of 47 subjects will be included and analyzed to support CE marking. The sample size of 47 subjects is considered adequate to assess the primary endpoint, which is defined as the proportion of subjects who experienced access/deployment failure or MDE within 30-days post index procedure.

Based upon the reported events from the VALOR II study on the Valiant Xcelerant stent graft system, the primary endpoint defined by this protocol would have a failure rate of 5.6% (9/160) within 30 days post index procedure. Considering the failure rate of Valor II, it is expected that Valiant Evo would perform similarly, meaning that 3 out of 47 subjects (6.4%) would likely fail within 30 days of implantation. The precision of this assumed 6.4% point estimate can be assessed by calculating the distance from the calculated 1-sided 95% upper confidence limit. This distance, or margin of error, is calculated to be <10% for this trial; therefore, considered adequate to assess the primary endpoint.

Due to sampling variation, different number of MDEs, anywhere from 0 to 47, might be observed, which would result in different confidence intervals depending on the outcomes as shown in Table C-1.

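### In protocol H.1, the sentence prescribing the exact interval for the regulatory submission defines the primary endpoint as MDE only, in conflict with the composite in the synopsis, C.2.1 and C.7 and with H.1's own reference to C.2

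*Protocol*

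**What the plan says.** The endpoint is defined in full in three places.

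- **Synopsis:** a composite of access and/or deployment failure with "b) Major device effect (MDE) within 30 days post index procedure".
- **C.2.1:** the same composite, with "a) Access and/or deployment failures; and/or" as its own limb beside the MDE limb.
- **C.7:** the sample size is judged adequate for the primary endpoint, "which is defined as the proportion of subjects who experienced access/deployment failure or MDE within 30-days post index procedure".

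H.1 mentions the primary endpoint in three ways.

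- **General paragraph:** "Event rates corresponding to the primary endpoint of the study will be analyzed by calculating the distribution frequencies", with exact one-sided 95% limits. The components are not listed.
- **Analysis for the Regulatory Submission, interval sentence:** "For the primary endpoint, which is defined as the proportion of subjects experiencing an MDE within 30 days post-implantation", followed by the Clopper-Pearson method.
- **Same subsection, closing line:** "Endpoints will be analyzed for these 47 included subjects as defined in Section C.2".

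L.2.1 defines access failure and deployment failure as separate terms. It lists four MDEs: device-related secondary procedure, device-related mortality, conversion to open surgery, and thoracic aortic aneurysm rupture.

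SAP 7.9 also scores a subject as a failure for either an access/deployment failure or an MDE. SAP section 3, however, says the plan is written for the US trial, used together with the international data, and names the US protocol as its primary resource.

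**The concern.** The H.1 sentence is worded as a definition and sits where the CE-mark analysis is specified. Programmed as written, it removes from the numerator every subject whose only event is an access or deployment failure. It can lower the reported failure rate or leave it unchanged, but it cannot raise it, because every MDE is also a composite event.

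The omitted limb bears directly on the trial's purpose. C.1.1 says the study is designed to assess the design changes from the predecessor device, and B.1 lists among these a lower delivery profile, a shorter tapered tip and tip capture on the Closed Web configuration. Access and deployment failures measure delivery performance most directly. An MDE-only result would also be set beside a reference rate that C.7 derived for the composite.

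**Working it through.** **1. Are the two definitions equivalent?** Take a subject in whom arterial access is established and insertion is attempted, but the device cannot be inserted. There is no conversion, rupture, device-related death or device-related secondary procedure.

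- F.1 counts this subject as included.
- L.2.1 calls the event an access failure.
- C.2.1 scores a failure. The H.1 interval sentence scores a success.

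The definitions therefore differ. They do overlap: a deployment failure that leads to primary conversion is already an MDE through the conversion component.

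**2. Reproduce the plan's figures.** Inputs: n = 47 and a 5.6% rate (C.7); exact Clopper-Pearson limits (H.1 and the Table C-1 note).

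- With X ~ Binomial(47, 0.056): P(X ≤ 3) = 0.7314 and P(X ≥ 6) = 0.0463, as stated.
- The one-sided 95% upper limit for k events is the 0.95 quantile of Beta(k+1, 47−k). For k = 0 this is 1 − 0.05^(1/47) = 6.18%.
- For k = 3 the limit is 15.68% and the two-sided interval is 1.3% to 17.5%, as stated.
- The margin of error is 15.68 − 6.38 = 9.30 points, below the 10 points in C.7.

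**3. Effect of one composite event not counted.** The rate falls by 1/47 = 2.1 points. The limit falls by the difference between adjacent rows (differences taken before rounding):

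| Composite events k | Limit at k | Limit at k−1 | Drop (points) |
|---|---|---|---|
| 1 | 9.70% | 6.18% | 3.53 |
| 2 | 12.80% | 9.70% | 3.10 |
| 3 | 15.68% | 12.80% | 2.88 |
| 4 | 18.43% | 15.68% | 2.75 |
| 5 | 21.08% | 18.43% | 2.65 |
| 6 | 23.65% | 21.08% | 2.57 |

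At the event count that C.7 expects, 3/47 = 6.4% (limit 15.7%, two-sided 1.3% to 17.5%) becomes 2/47 = 4.3% (limit 12.8%, two-sided 0.5% to 14.5%).

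**4. How often might this happen?** The documents do not split the 9 reference events, so this step rests on an assumption. Let s be the share of composite failures that are access-only or deployment-only, with a true composite rate of 5.6% (47 × 0.056 = 2.63 expected events). Expected number not counted = 47 × 0.056 × s. Chance of at least one = 1 − (1 − 0.056s)^47.

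| Assumed s | Expected not counted | P(at least one) |
|---|---|---|
| 0% | 0 | 0 |
| 10% | 0.26 | 0.23 |
| 25% | 0.66 | 0.48 |
| 50% | 1.32 | 0.74 |

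**5. Comparability with the reference.** If x of the 9 reference failures had no MDE (again an assumption), the matching MDE-only reference is (9 − x)/160.

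- x = 0: 5.6%, 47 × 9/160 = 2.64 events expected in 47.
- x = 3: 6/160 = 3.75%, 1.76 expected.
- x = 6: 3/160 = 1.9%, 0.88 expected.

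An MDE-only result could be compared fairly with 5.6% only if x = 0.

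**The case against.** The strongest reply is that no careful reader would adopt the MDE-only definition. The closing line of the same subsection points to C.2, and each full definition in the protocol is the composite. The Table C-1 note also names Clopper-Pearson as the method for the data analysis, in a table built on the composite rate, so the interval method does not depend on the disputed sentence. MDE is used as shorthand elsewhere: C.7 speaks of a varying count of MDEs, the Table C-1 note labels 5.6% an MDE rate, and F.6.1 says MDEs serve to assess the primary endpoint. That pattern suggests a drafting habit, not a rival endpoint. SAP 7.9 shows the same composite understanding across the programme.

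Most of this stands, and it makes a slip the likely explanation. It does not remove the conflict. The C.2 reference shows which definition is intended but leaves the other in place, and the H.1 sentence presents itself as a definition, unlike the shorthand elsewhere. The SAP is written for the US and pooled analysis, so it does not settle the analysis of the 47 subjects.

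A reader might infer more than the documents support:

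- **That H.1's general paragraph is contradicted too.** It names the primary endpoint without its components, so it is neutral.
- **That the 5.6% or Table C-1 is MDE-only and needs recalculation.** C.7 ties 9/160 to the primary endpoint as the protocol defines it, and the table reproduces from that rate.
- **That treatment failures leave the analysis because it is timed** "when the first 47 subjects have been implanted with the study device for at least 30 days". H.1 analyses all included subjects, the closing line again says included, and L.3.3.4 caps enrolment at 47. The timing phrase is loose wording only.

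**Conclusion.** The inconsistency is real and should be corrected. Two incompatible definitions of the primary endpoint stand in one subsection of H.1, and the MDE-only one is wrong against the synopsis, C.2.1 and C.7.

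The effect of 2.1 points in the rate and 2.6 to 3.5 points in the one-sided limit applies per affected subject, for 6 down to 1 composite events. It holds only if the sentence is programmed literally with 47 as denominator. The number of such subjects cannot be derived from the documents and may be zero; the shares in step 4 illustrate a range and do not predict.

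C.3 and H.1 state that the trial has no hypothesis and no pass/fail criterion. The consequence is therefore a possibly understated rate and limit in the submission, not a changed decision. Sample size, the stated precision and every Table C-1 figure are unaffected.

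**What to change.** - **H.1, Analysis for the Regulatory Submission:** define the primary endpoint as the proportion of included (mITT) subjects with an access and/or deployment failure and/or an MDE within 30 days of the index procedure. Alternatively, delete the definition and refer only to C.2.1.
- **C.7, Table C-1 note and F.6.1:** replace the MDE shorthand with primary endpoint (composite) events and rate. In F.6.1, say that MDEs are one limb of the primary endpoint.
- **Minor, same edit:** time the analysis on the 47 included subjects having reached 30 days after the index procedure or died earlier, in place of subjects implanted.

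The cost is protocol wording only. No new data are needed: F.2.2 already follows treatment failures for 30 days, and L.2.3 already lists access failure and deployment failure as device deficiencies on the case report form.
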